6.4. Covariates

Log-transformed 28-day seizure rate [$\log_e(28\text{-days seizure rate}_b + 1)$] at baseline will be utilized as a covariate in the linear model used in the primary analysis, and for secondary analyses utilizing a similar model.

Additional terms considered in the primary analysis and included in the responder rate analysis are age strata and geographic region. Because it is anticipated that this study will have many investigator centers having very few subjects in each treatment group, age strata, and geographic region combination; a pre-specified pooling will take place (See [below](#)).

Two covariates about age are defined as follows.

Age strata will be defined as Stratum 1: 5-7 years of age; Stratum 2: 8-11 years of age; Stratum 3: 12-16 years of age; or Stratum 4: 17-65 years of age. This covariate is applied to primary analysis.

Age group will be defined as: group 1, 5-16 years of age (at randomization); group 2: 17-65 years of age (at randomization). This covariate is applied to the analysis of primary efficacy endpoint as a sensitivity analysis. This age group definition will also be used to investigate treatment-by-age interaction for the primary efficacy endpoint.

Age will be defined as subjects' age at randomization. If a subject turns 66 at randomization after screening, he/she will be counted in the 17-65 age group.

Region will be defined as follows (Upon closing of the randomization, region determinations will be further evaluated-See [contingency plan](#)):

- *United States (US)*: Subjects who participate in the U.S. or Puerto Rico centers will be pooled together;
- *European Union*: All subjects who participate in European Union (eg, Austria, Belgium, Denmark, France, Germany, Greece, Italy, Netherlands, Portugal, Spain, Sweden, United Kingdom, Bulgaria, Croatia, Czech Republic, Estonia, Hungary, Lithuania, Poland, Romania, and Slovakia,) centers will be pooled together. The member countries of European Union are explained in more detail at https://europa.eu/european-union/about-eu/countries_en;
- *Asia-Pacific*: All subjects participating in Asia-Pacific (China, India, Korea, Malaysia, Philippines, Singapore) centers will be pooled together;
- *Others*: All subjects not participating in above three regions (eg, Russian Federation, Ukraine, Belarus, Bosnia and Herzegovina, Serbia, Montenegro, Turkey) centers will be pooled together.

Any region not enrolling any subjects will not be included in the analysis.

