7. HANDLING OF MISSING VALUES

Missing data will be handled based on the nature of the endpoint and the proposed statistical methods for analyzing the data.

For all endpoints that include seizure rate, days with missing seizure diary data will be subtracted from the seizure rate calculations. If seizure rate for any phase cannot be calculated for a subject due to missing information, the endpoint that involves seizure rate during that phase will be also missing for that subject.

For scales used in this study, scores will be imputed according to the imputation rules and algorithms for missing component scores that are provided in the data standard documents. Partial dates for AEs and concomitant medications will be imputed according to Pfizer standard algorithms.

The assessment of missing data for the primary endpoint will require the construction of the following windows and drop-out categories:

- *Windowing for each subject will be constructed for the 1st month, 2nd month, and 3rd month the subject was in the study. Thus a 28-day seizure rate will be determined for each windowed month for which seizure data exist, otherwise the seizure data will be considered missing with a corresponding reason for it being missing. Specific details are provided in [Appendix 3](#).*
- *Drop-out patterns will be constructed based on the reason the seizure data is missing for the corresponding windowed month. Hence, the following drop-out patterns will be defined for three specific categories of related to lack of efficacy or adverse event or other reason:*
 - *Completed study as planned.*
 - *Drop-out due to lack of efficacy:*
 - *Drop-out at month 1 due to lack of efficacy;*
 - *Drop-out at month 2 due lack of efficacy;*
 - *Drop-out at month 3 due to lack of efficacy.*
 - *Drop-out due to an adverse event:*
 - *Drop-out at month 1 due to an adverse event;*
 - *Drop-out at month 2 due to an adverse event;*
 - *Drop-out at month 3 due to an adverse event.*
 - *Drop-out due to other reason:*
 - *Drop-out at month 1 due to other reason;*
 - *Drop-out at month 2 due to other reason;*
 - *Drop-out at month 3 due to other reason.*

Other reason includes any drop-outs excluding efficacy and adverse event.

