A supplemental analysis will be performed to investigate generalizability of the treatment difference with respect to the 2 age categories (ie, a possible treatment-by-age interaction that is statistically and clinically relevant). The estimated seizure rate, standard error and the corresponding 95% confidence interval in addition to the treatment difference between each pregabalin treatment group and placebo will be calculated for both pediatric (5-16 years of age) and adult population (17-65 years of age). This supplemental analysis will also be a re-evaluation of the primary analysis model with an interaction term for treatment-by-age. This model will not replace the primary model.

As a supplemental analysis, a generalized linear model assuming a Poisson and negative binomial distributions and canonical log link function will be applied to the raw seizure counts.^{1,2} The model will have an off-set parameter for the amount of time (i.e., $\log_e(\text{days})$) the subject was in the double blind treatment phase. A scale parameter of Pearson will be specified to fit the Poisson distribution.

The analyses with Poisson and negative binomial models will be performed with baseline seizure count as covariate.

The raw 28-day seizure rate will be summarized overall, and separately by age group of pediatrics overall (<17 years) and adults (17-65 years).

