Log _e 28-day PGTC seizure rate (N, LS Mean Diff/SE)	ITT	ANCOVA	Treatment, region, 2 age groups , baseline	Days missing from Seizure Diary will be subtracted from rate calculations	Sensitivity Analysis Note: age group are Age< 17 yrs and Age>= 17 yrs. Baseline is the log of 28-day PGTC rate at baseline
Log _e 28-day PGTC seizure rate (N, LS Mean Diff/SE)	ITT	ANCOVA	Treatment, pooled region, 2 age groups , baseline	Days missing from Seizure Diary will be subtracted from rate calculations	Sensitivity Analysis Note: age group are Age< 17 yrs and Age>= 17 yrs. US and European Union will be pooled in the region class. Baseline is the log of 28-day PGTC rate at baseline
Change from baseline to double blind phase of Log _e 28-day PGTC seizure rate	ITT	Rank ANCOVA	Treatment, region, age strata, region and ranked log-BL		Sensitivity Analysis (Log-Scale). Baseline is the ranked log of 28-day PGTC rate at baseline.
Change from baseline to double blind phase of Log _e 28-day PGTC seizure rate (DB Phase)	ITT	Wilcoxon-Mann Whitney Test			Sensitivity Analysis (Log-Scale)
Raw Seizure Count	ITT	GENMOD, Poisson and negative binomial distribution with log link	Treatment, and baseline		scale parameter = Pearson for the Poisson model. Baseline for this endpoint is seizure count at baseline.

- All efficacy endpoints will be presented descriptively overall, and separately as by age group of pediatrics overall (<17 years) and adults (17-65 years).

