Appendix 1. Data Derivation Details

This table describes how seizure related endpoints have been defined.

Endpoint	Derivation
8-week baseline phase (b) 28-day seizure rate	28-day seizure rate _b = [(# of seizures _b) ÷ (#of days _b - # of missing diary _b)] × 28, where #of days _b is defined as (first dose date-1) – screening date +1.
12-week double-blind treatment phase (t) 28-day seizure rate	28-day seizure rate _t = [(# of seizures _t) ÷ (#of days _t - # of missing diary _t)] × 28, where #of days _t is defined as date of last dose in phase – date of first dose in phase +1.
Primary endpoint : Log _e of 28-day seizure rate during 12-week double-blind treatment phase	Log _e (28-day seizure rate _t +1)
“Percent reduction in seizures” relative to placebo	
For example, a difference between one of the pregabalin doses and placebo of -0.400 on the log transformed scale for the 28-day seizure rate translates into a 33% reduction in the 28-day seizure rate of the pregabalin group from the placebo group (ie, 100%*[exp-0.400-1] = -33%)
 
An additional back transformation will be calculated for the percent reduction in seizures for each pregabalin treatment group relative to placebo for presentation in the CSR as follows:
 $100\% \times \frac{\exp(\text{LSMean(pregabalin)}) - 1 - [\exp(\text{LSMean(placebo)}) - 1]}{\exp(\text{LSMean(placebo)}) - 1}$
Percent change from baseline in 12-week 28-day seizure rate	% Change = [28-day seizure rate _t - 28-day seizure rate _b] / 28-day seizure rate _b] × 100%
Responders	
≥50% reduction in the 28-day seizure rate from baseline during the 12-week double-blind treatment phase, then response = 1 (responder) otherwise response = 0 (non-responder).
 
The response status will be set as missing if the baseline seizure rate is missing. If baseline seizure rate is non-missing but there are no double-blind phase seizure rates, then the response status will be set as non-response

Proportion Seizure-free days	The numerator for seizure-free days is defined as the number of days the subject experience no seizures over the double-blind assessment phase.

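### The supplemental Poisson and negative binomial models enter the baseline seizure count unlogged under a log link, which costs precision if baseline rates are widely spread

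*SAP*

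**What the plan says.** SAP Section 8.1, under Supplemental Analysis, plans Poisson and negative binomial models and describes the link and outcome thus: "canonical log link function will be applied to the raw seizure counts". On exposure it says "The model will have an off-set parameter for the amount of time" spent in the double-blind treatment phase, with a Pearson scale for the Poisson fit. On baseline it says "The analyses with Poisson and negative binomial models will be performed with baseline seizure count as covariate". The last row of the Section 8.5 table agrees: "Baseline for this endpoint is seizure count at baseline". Appendix 5 sets out the link and the offset but adds no log, rate or run-in adjustment for the covariate.

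Elsewhere the SAP handles baseline differently. Section 6.4 says that the log-transformed baseline 28-day rate, log_e(rate + 1), "will be utilized as a covariate in the linear model used in the primary analysis". The imputation models in Section 8.1 and Appendix 4 use the same variable. Appendix 1 derives the baseline rate from subject-specific days, "first dose date-1) – screening date +1", less missing diary days, and Section 7 says "days with missing seizure diary data will be subtracted from the seizure rate calculations".

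The amendment log (Amendment 2, item 11) gives two reasons for the count covariate: consistency with A0081042, and adjustment for baseline seizure imbalance.

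**The concern.** With a log link and a raw count, the fitted rate is exp(a + b × count), so equal steps in the count multiply the expected rate by equal factors. Stable disease suggests instead that the double-blind rate is roughly proportional to the baseline rate, which means a covariate on the log scale. Seizure counts are usually skewed. A few subjects with very high baseline counts can then dominate the estimate of b, and the covariate explains less of the variation among everyone else.

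What is at stake is the precision of the supplemental count analyses. These are the only planned models of the seizure counts themselves. A wider interval than necessary makes them less useful as support for the primary result, and the baseline adjustment that the amendment log asks for is done less well.

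**Working it through.** **1. The plan's own figures.** The SAP gives no power or precision for the count models, only for the primary comparison (Section 2.2, Table 1). With 56 per group, 2-sided α = 0.05 and 110 df, a two-sample noncentral t calculation gives the following power.

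| Difference | SD | Recomputed | Table 1 |
|---|---|---|---|
| −0.534 | 0.73 | 0.970 | 0.970 |
| −0.534 | 0.67 | 0.987 | 0.984 |
| −0.358 | 0.73 | 0.730 | 0.742 |
| −0.358 | 0.67 | 0.800 | 0.800 |

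All agree within 0.02. The normal formula n = 2(1.960 + 0.842)² × SD² / 0.358² gives 55 per group at SD 0.67 (planned 56) and 64 at SD 0.72 (cap 65). The design inputs therefore reproduce and can anchor a simulation.

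**2. The shape of the two covariates.** Suppose a baseline of 6 seizures in 56 days (3 per 28 days), and choose b so that going from 6 to 12 doubles the expected rate: b = ln 2 / 6 = 0.1155. The raw-count model then multiplies the rate by exp(0.1155 × 12) = 4 from 12 to 24, and by exp(0.1155 × 24) = 16 from 24 to 48. A proportional relation gives a factor of 2 at every doubling. The covariate log(rate + 1) comes close: as the rate goes 3, 6, 12, 24 its steps are 0.56, 0.62 and 0.65, against a constant 0.69 for a pure log.

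**3. Simulation inputs.** From the SAP: 56 per arm, an 84-day double-blind phase, effects −0.358 and −0.534, and a log(days) offset. Assumed, because the SAP does not give them:
- lognormal baseline rates, median 3 per 28 days, log SD 0.4 to 1.2;
- at least 2 baseline seizures;
- run-in fixed at 56 days or uniform over 42 to 63;
- 15% early dropout;
- extra within-subject log SD 0.85, which gives an ANCOVA residual SD of 0.63 to 0.67, near the planning value;
- follow-up rate proportional to baseline rate.

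There were 300 runs per scenario.

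**4. Results for Dose Level 1.** The table shows the model-based SE of the log rate ratio with the raw count and with log(rate + 1), and the ratio of variances (raw over log). Ratios come from unrounded SEs.

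| Log SD | Run-in (days) | Poisson SE | Ratio | Neg. bin. SE | Ratio |
|---|---|---|---|---|---|
| 0.4 | 56 | 0.199 / 0.197 | 1.02 | 0.183 / 0.183 | 1.00 |
| 0.7 | 42–63 | 0.204 / 0.197 | 1.07 | 0.187 / 0.184 | 1.03 |
| 1.0 | 42–63 | 0.220 / 0.192 | 1.32 | 0.192 / 0.182 | 1.11 |
| 1.2 | 42–63 | 0.236 / 0.189 | 1.55 | 0.199 / 0.182 | 1.20 |

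In interval width, √1.55 = 1.24 and √1.20 = 1.10, so at the widest spread the intervals are about 24% and 10% wider. Model-based SEs were below the empirical SDs under both covariates, but the empirical variance ratios show the same pattern: 1.02 to 1.51 for Poisson and 1.01 to 1.25 for negative binomial.

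**5. Power at −0.534, raw count against log rate.** At log SD 0.7 (run-in 42–63), Poisson was 65% against 66% and negative binomial 74% against 77%. At log SD 1.2, Poisson was 50% against 67% and negative binomial 72% against 78%. The Monte Carlo standard error of each figure is up to about 3 points (√(0.5 × 0.5 / 300) = 0.029).

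**6. Which part of the change matters.** Log(count + 1), which is logged but not normalised, has variance within about 2% of log(rate + 1). The raw 28-day rate, which is normalised but not logged, still has ratios of 1.51 (Poisson) and 1.20 (negative binomial) at log SD 1.2. The reason is simple. A run-in uniform over 42 to 63 days has SD 21/√12 = 6.1 around a mean of 52.5, a relative SD of about 0.12, which is small beside a log SD of 0.4 to 1.2 between subjects.

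**The case against.** The strongest counter-case has four parts.

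*The size rests on an unknown.* The SAP does not state the spread of baseline PGTC rates, and at log SD 0.4 there is almost no loss. The simulation also makes follow-up proportional to baseline, so the raw-count model is misspecified by construction. This stands: only a range can be given, and it is conditional on that assumption.

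*A reader might quote a single large power loss.* With log SD 1.1, effect −0.40 and within-subject log SD 0.45, Poisson power was 61% with the raw count against 75% with the log rate. That is one unfavourable setting for one of the two models. Negative binomial gave 75% against 83% there. With a residual SD near 0.69 and effect −0.534, Poisson gave 65% against 74%. The SAP has nothing that would single out any of these as the expected loss.

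*A reader might treat the missing run-in normalisation as an equal defect.* Unequal run-in days do give subjects with the same frequency different covariate values. But the SAP plans an 8-week baseline for everyone and reports no large variation in run-in or missing baseline diary days, and step 6 of the working shows that normalising adds little near 8 weeks. It would matter more only if run-ins proved long or uneven, or if many diary days were missing.

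*The models are supplemental and the choice was deliberate.* The decision rules in Section 4.2 rest on the primary endpoint alone, the ANCOVA already uses the log baseline rate, and several other sensitivity analyses are planned. Consistency with A0081042 is a legitimate reason. This limits the priority of the point but does not remove it, because both versions can be reported. A reader might also infer that the count models will be biased or will contradict the primary result. The documents do not support that: randomisation protects the comparison from systematic bias whatever the covariate's form, and a wider interval is not a contradiction.

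**Conclusion.** The point holds as a matter of efficiency in supplemental analyses. If baseline rates are lognormal and follow-up rates are proportional to them, the raw count inflates the variance of the treatment effect by about 2% to 55% under Poisson and 0% to 20% under negative binomial, for log SDs of 0.4 to 1.2. The loss is negligible for homogeneous baseline rates and clear from a log SD of about 1.0. It comes almost entirely from leaving the covariate unlogged. The primary analysis, its type I error, power and sample size are untouched. The improvement is worthwhile but optional.

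**What to change.** In Section 8.1 (Supplemental Analysis) and in the raw seizure count row of Section 8.5, replace the baseline seizure count in both count models with log_e(28-day baseline PGTC rate + 1). Cite the Section 6.4 formula as well as the program name LN_BSZRT, because the variable list in Appendix 4 prints the treatment-phase subscript against that name. This one covariate does the logging and also normalises for run-in days less missing diary days.

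The cost is one variable name in the SAP and the program, since the variable already exists. The real trade-off is a departure from the form adopted for consistency with A0081042. Reporting the raw-count fit next to the revised one keeps that comparison. The change should be made before unblinding.

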2.1. Study Design

This study will consist of an 8-week baseline phase, a 12-week double-blind assessment phase (including a 2-week double-blind dose escalation phase and a 10-week double-blind fixed dose phase), and a 1-week double-blind taper phase. Eligible subjects will be randomly assigned to receive double-blind treatment with 1 of 2 dose levels of pregabalin or placebo. Study drug treatments are to be taken orally twice daily (BID) in equally divided doses for 12 weeks during the double-blind assessment phase and then 1 week double-blind taper. Subjects who complete the double-blind phase of this trial may be eligible for screening for a 1-year open-label pregabalin safety study.

A total sample size of 168 subjects (ie, 56 subjects per group) is needed to have been randomized, received treatment and had a baseline and post baseline efficacy assessment. Randomization will be stratified by site and subject age (Stratum 1: 5-7 years of age; Stratum 2: 8-11 years of age; Stratum 3: 12-16 years of age; Stratum 4: 17-65 years of age). Subjects in each age stratum within site will be randomized to a fixed dose of either placebo, Dose Level 1: pregabalin 5 mg/kg/day (maximum 300 mg/day) or Dose Level 2: pregabalin 10 mg/kg/day (maximum 600 mg/day) in a 1:1:1 ratio. Approximately 30% of planned enrollment (approximately 50 subjects) will be subjects <17 years of age. Every reasonable effort will be made to enroll a minimum of 12 subjects in each of the 4 age strata.

Study Design Diagram:

*Eligible subjects may be assessed for a 1-year open-label pregabalin safety study (Study A0081106) and complete end of study activities for A0081105 at Visit 10 (V10).

** Dose Level 1: 7 mg/kg/day for pediatric subjects <30 kg and 300 mg/day for subjects ≥ 17 years of age.

*** Dose Level 2: 14 mg/kg/day for pediatric subjects <30 kg and 600 mg/day for subjects ≥ 17 years of age.

Phone visits are also scheduled for Study Days 3, 10, 17, and 89 (each with a ± 3 day window).

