4. HYPOTHESES AND DECISION RULES

4.1. Statistical Hypotheses

There will be 2 pair-wise comparisons of interest:

- a) Dose Level 2: pregabalin 10 mg/kg/day (maximum 600 mg/day) - placebo, and*
- b) Dose Level 1: pregabalin 5 mg/kg/day (maximum 300 mg/day) - placebo.*

Each dose of pregabalin will be compared to placebo in a pair-wise manner using a sequential step-wise testing procedure to control for multiplicity of testing such that the experiment-wise type I error rate will not exceed the 5% level of significance.

1) The first step will test the null hypothesis of equal treatment effect of Dose Level 2 vs. placebo at $\alpha=0.05$ 2-sided for the primary endpoint.

$$H_{01}: \mu_{\text{PGB Dose Level 2}} - \mu_{\text{PBO}} = \mathbf{0}$$

$$H_{a1}: \mu_{\text{PGB Dose Level 2}} - \mu_{\text{PBO}} \neq \mathbf{0}$$

2) The second step will test the null hypothesis of equal treatment effect of Dose Level 1 vs. placebo at $\alpha=0.05$ 2-sided for the primary endpoint.

$$H_{02}: \mu_{\text{PGB Dose Level 1}} - \mu_{\text{PBO}} = \mathbf{0}$$

$$H_{a2}: \mu_{\text{PGB Dose Level 1}} - \mu_{\text{PBO}} \neq \mathbf{0}$$

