Other analyses of continuous dependent variables with ANCOVA model will follow the same procedure as the primary efficacy endpoint analysis. Responder rates and any other binary variables that use the same planned model as primary efficacy endpoint analysis will similarly be adjusted as needed.

Sensitivity Analysis

As a sensitivity analysis of the primary endpoint, multiple imputation methods will be used to evaluate the impact of missing data (See [Appendix 4](#)).

Subjects who discontinue the study for insufficient clinical response, adverse event, or death will be imputed based on the observed placebo distribution, regardless of randomized treatment assignment. Imputation will be based on baseline $\log_e(28\text{-days seizure rate}_b + 1)$, geographical region, baseline weight (continuous), and age strata.

Subjects who discontinue the study for other reasons, or who complete the study but have a missing double blind seizure rate, will be imputed based on observed subjects in the same randomized treatment group. Imputation will be based on treatment group, baseline $\log_e(28\text{-days seizure rate}_b + 1)$, geographical region, baseline weight (continuous), and age strata.

A sensitivity analysis will be performed using the same linear model as the primary efficacy analysis except for the age covariate, which will be applied for the 2 age groups (5-16 years of age; 17-65 years of age).

An additional sensitivity analysis will be performed using the same linear model as the primary efficacy analysis with two age groups covariate as well as pooled region of US and European Union.

A ranked ANCOVA will be performed for the change from baseline to double blind phase of log-transformed (\log_e) 28-day seizure rate for all PGTC seizures, including age strata, treatment group, and region.

A Wilcoxon-Mann Whitney test will also be performed and reported for the change from baseline to double blind phase of log-transformed (\log_e) 28-day seizure rate for all PGTC seizures.

Supplemental Analysis

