Appendix 6. Blinded Sample Size Re-Estimation

The proposed sample size re-estimation formula (Friede and Keiser, 2011)³ is the following:

$$n^* = \frac{(1+\gamma)^2 \cdot (z_{1-\alpha/2} + z_{1-\beta})^2 \cdot (1-\rho^2) \cdot \sigma^2}{\gamma \Delta^2}$$

where,

n^* is the revised total sample size of two treatment groups for this estimation;

γ is the ratio of the estimated sample size of two treatment groups;

$z_{1-\alpha/2}$ is a percentile from a standard normal cdf with $\alpha/2=0.025$;

$z_{1-\beta}$ is a percentile from a standard normal cdf with $\beta=0.20$;

σ^2 is the blinded estimate of pooled variance for outcome variable at the interim review;

ρ is the blinded estimate for the correlation between an outcome and a covariate variable;

Δ is the clinically meaningful difference between *Dose Level 1: pregabalin 5 mg/kg/day (maximum 300 mg/day)* and placebo (i.e., 0.358) as specified in the protocol.

For this study, the ratio of estimated sample size of two treatment group (γ) is assumed as one due to 1:1 randomization with respect to placebo versus dose level 1. In addition, the estimates for correlation (ρ) and pooled variance (σ^2) is estimated based on the residual variance of ANCOVA. Therefore, the simplified equation for this study is:

$$n^* = \frac{4 \cdot (z_{1-\alpha/2} + z_{1-\beta})^2 \cdot \tilde{s}^2}{\Delta^2}$$

where,

\tilde{s}^2 is the blinded estimate of the residual variance based on ANCOVA at the interim review.

The pooled blinded estimate of the variance, \tilde{s}^2 , will be based in a blinded manner without making any correction for possible treatment group differences after the 1st 110 subjects have had the opportunity to complete the study. Since baseline 28 day seizure rate, age strata, and geographical region are important pre-specified modeling terms that explain sources of variability in the data, the estimate \tilde{s}^2 will take into consideration these three modeling terms as the mean squared error. While this pooled

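### The supplemental Poisson and negative binomial models omit age and region, which the other efficacy regressions carry; this may cost some precision and blurs the comparison with the primary ANCOVA.

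*SAP*

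**What the plan says.** SAP Section 8.1 (Supplemental Analysis) fits Poisson and negative binomial models to the raw seizure counts with a log link and an offset for time in the double-blind phase. On covariates it says: "The analyses with Poisson and negative binomial models will be performed with baseline seizure count as covariate". On overdispersion it says: "A scale parameter of Pearson will be specified to fit the Poisson distribution". The Raw Seizure Count row of Section 8.5 lists the model terms as "Treatment, and baseline". Appendix 5 describes the offset and the Pearson scale and adds no covariate. No section puts age or region into either model.

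On the design, Section 2.1 says: "Randomization will be stratified by site and subject age". Age has four strata. Region (Section 6.4) pools investigator centres, so it is a coarse version of the site stratum. Appendix 6 describes baseline seizure rate, age strata and region together as "important pre-specified modeling terms that explain sources of variability in the data", and removes all three from the blinded variance estimate used for sample size re-estimation.

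**The concern.** Suppose randomisation balances the arms on a factor that predicts the outcome, and the model omits that factor. The factor's variation then stays in the Pearson scale (Poisson) or the dispersion parameter (negative binomial). The treatment contrast does not really carry that variation, because the arms are balanced, but the reported standard error does. The interval is then wider than it needs to be.

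Interpretation also suffers. The count models are the only planned inferential models of the raw counts, and they help to show whether the result depends on the log(rate + 1) ANCOVA. Such a check is easiest to read when it changes one thing. Here the distribution and the covariate set change together. If the ANCOVA and the count models disagree, a reader could not tell from the planned output which change caused it.

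**Working it through.** **1. Covariates side by side (SAP Sections 8.1, 8.2, 8.5).**

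| Model | Age term | Region |
|---|---|---|
| Primary, multiple-imputation and rank ANCOVA | four strata | yes |
| Responder and seizure-freedom logistic | four strata | yes |
| Seizure-free days (proportion; days gained) ANCOVA | four strata | yes |
| Treatment-by-age ANCOVA | two groups | yes |
| Sensitivity ANCOVA with age group | two groups | yes |
| Sensitivity ANCOVA with age group and pooled region | two groups | US and EU pooled |
| Poisson, negative binomial | none | none |
| Wilcoxon-Mann Whitney test (not a regression) | none | none |

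**2. The plan's own figures.** The SAP states no precision or power for the count models. Its only power figures are in Table 1, for the log-scale endpoint. With 56 per group and two-sided 0.05, power = Φ(δ / (SD × √(2/56)) − 1.96):
- δ = 0.534: 0.972 (SD 0.73) and 0.988 (SD 0.67), against 0.970 and 0.984 stated.
- δ = 0.358: 0.737 (SD 0.73) and 0.807 (SD 0.67), against 0.742 and 0.800 stated.

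Table 1 reproduces to within one point and does not bear on this question.

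**3. Break-even in a linear analogue.** Take N = 168. Intercept, two treatment terms and baseline leave 164 residual degrees of freedom. Three age and three region parameters reduce this to 158. If R² is the sample partial R² of the six terms, then

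interval width ratio (with / without) = √[(1 − R²) × 164/158] × t(0.975; 158)/t(0.975; 164) = √(1 − R²) × 1.0191.

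| R² | 0 | 2% | 3.7% | 5% | 10% | 20% |
|---|---|---|---|---|---|---|
| Ratio | 1.019 | 1.009 | 1.000 | 0.993 | 0.967 | 0.912 |

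If the six terms are pure noise, their expected sample R² is 6/164 = 3.7%, which is the break-even point. Uninformative terms therefore cost about nothing on average, although a single trial's interval can widen slightly.

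**4. Simulation of the count models.** From the SAP: 56 per arm, a Dose Level 1 effect of −0.358, about 50 subjects under 17, at least 12 per age stratum as the target, and 5 US subjects. Assumed: the detailed age mix (12/14/24/118), the region mix (5/60/40/63), gamma-Poisson counts over three months with dispersion 0.45, and the share of between-subject variance due to age and region. There were 1000 trials per scenario. Ratios are medians of the Dose Level 1 standard error with the terms over without them.

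| Assumed share | Poisson SE ratio | Poisson power | Neg. binomial SE ratio | Neg. binomial power |
|---|---|---|---|---|
| 0% | 1.004 | 0.634 → 0.633 | 0.999 | 0.625 → 0.625 |
| 10% | 0.951 | 0.599 → 0.634 | 0.966 | 0.593 → 0.621 |
| 18% | 0.898 | 0.543 → 0.626 | 0.934 | 0.552 → 0.603 |

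This simulation adjusted for log baseline rate, whereas the SAP specifies baseline count. Two Poisson repeats with the raw count gave ratios of 0.943 and 0.957 at a 10% share, and 0.903 and 0.922 at 18%. The choice does not change the conclusion.

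**5. A second set of assumptions.** This used raw baseline count, dispersion 0.6, randomisation stratified by age and 200 trials per setting. Poisson / negative binomial ratios were 1.003 / 0.999 with no prognostic effect, 0.979 / 0.986 with a weak one, 0.904 / 0.942 with a moderate one and 0.658 / 0.797 with a strong one. The adjusted standard error was the larger in 57% / 49% of trials with no effect, 27% / 22% with a weak effect and 2.5% / 2.5% with a moderate one. The strong setting is an extreme assumption that nothing in the documents supports.

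**The case against.** The case for leaving the models alone has several parts.

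- **The gain is not established.** It needs age and region to predict counts after baseline count is fitted. Appendix 6 names the three terms jointly, for the log-scale ANCOVA, and gives no size. This stands: a reader might infer that the intervals will be wider than necessary, but the documents support only that they may be.
- **Not every other analysis uses the four age strata.** This also stands. Three ANCOVAs use two age groups, the Wilcoxon test has no covariates, and region is not itself a randomisation stratum. The contrast is with the other regression models, which carry some age term and region.
- **There is a stated reason.** The amendment log (Section 1, Amendment 2, item 11) ties baseline count and the Pearson scale to consistency with A0081042 and to baseline imbalance. That explains what was added, not what was left out. Item 9 gives the same two reasons for changing the rank ANCOVA, which still carries age strata and region.
- **Sparse cells.** The amendment log reports only 5 US subjects, and the Section 8.1 contingency plan covers ANCOVA and binary models, not count models. This is a fair point against adding the terms unaided. Extending the contingency answers it.
- **Limited role.** The count models are supplemental and outside the stepwise test, and the rank ANCOVA is another, fully adjusted check on log(rate + 1). This limits the priority.

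A reader might also infer that the Wilcoxon test should be stratified. An unstratified rank test is valid, an adjusted rank ANCOVA accompanies it, and nothing here quantifies a gain. No change is proposed there.

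**Conclusion.** The omission is clear from the SAP and is out of line with its other efficacy regressions, its randomisation and its own account of what explains variability. The possible loss of precision ranges from about nil, if the terms are not prognostic, to roughly 3-5% of the standard error at an assumed 10% share and 7-10% at an assumed 18%. In the main simulation that is about 3 points of power at 10% and 5 to 8 points at 18%, for analyses that have no power target. These sizes rest on assumed prognostic strength, dispersion and age and region mix. The difficulty in attributing a disagreement with the primary ANCOVA does not depend on those assumptions.

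A reader might go further and infer bias, an inflated error rate or a weakened primary result. The documents do not support that. A standard error that is too large makes the count-model test conservative, and the primary test already contains age strata and region. This is a low-priority improvement.

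**What to change.** In SAP Sections 8.1 and 8.5, add age strata and geographic region, coded as in the primary model, to both the Poisson and the negative binomial model. Extend the Section 8.1 contingency plan to them in the same words: pool the US with the European Union if the small region causes a model problem, use the two age groups if the strata do, and do both if both do. Make the change while the study is still blinded.

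The cost is a few lines of SAP text and up to six extra parameters (three for age, three for region). If the terms turn out to be uninformative, the change in standard error is negligible.
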